5.4 Withdrawal of Subjects from Study

5.4.1 Definitions

A 'completed' subject is one who has completed all phases of the study, including all follow-up visits specified.

A 'withdrawal' is a subject who stops prematurely for reasons related to the study, e.g. an AE. A subject who simply wishes to withdraw from the study should also be considered a withdrawal.

5.4.2 Subject Discontinuation or Withdrawal

Subjects are free to withdraw from participation in this study at any time, for any reason, specified or unspecified and without penalty or loss of benefits to which the subject is otherwise entitled.

Subjects may be withdrawn from the study by the Investigator at any time due to an AE or any other reason if it is the opinion of the Investigator that continued participation in the study is no longer in the best interest of the subject. These reasons include, but are not limited to the following:

- Adverse drug reaction or AE or any other reason for which, in the opinion of the Investigator, subject's continued participation in the study is not in the best interest of the subject
- Withdrawal of consent (subject must be withdrawn)
- Subject fails to return to the site and does not respond to the attempts of the investigational site to contact him (lost to follow-up)
- Protocol violation(s), such as non-compliance with study medication or visit schedule or treatment with prohibited concomitant medications
- Pregnancy (treatment with study drug, if during treatment phase, must be discontinued and subject must be withdrawn from the study)

Relapse of TTP on study (defined as *de novo* event of TTP that occurs later than 30 days after the last daily PE) is not considered a reason for study withdrawal. However re-initiation of study drug treatment as an adjunctive treatment to PE in case of TTP relapse is not permitted.

Subjects discontinuing study drug administration should be encouraged to remain in the study and complete the originally scheduled follow-up visits.

For all subjects withdrawing from the trial for whatever reason, all data will be collected, documented and reported. The case report form (CRF) must be completed up to the time of withdrawal and the Premature Termination Form must be completed. Except for subjects who refuse to return to the investigational site, all subjects withdrawn after at least one administration of study drug should undergo a post-study assessment.

In case of withdrawal from the study due to an AE, subjects should be followed by the Investigator until the AE has resolved.

5.4.3 Procedure for Handling Withdrawals and Replacements

All cases of premature termination, or exclusion of individual subjects, will be discussed with the Sponsor and it will be decided in consultation with the Sponsor whether this subject will need to be replaced. Subjects withdrawn due to adverse drug reactions or adverse events will not be replaced.

If a withdrawal has to be replaced the replacement subject will undergo the same procedures and assessments as 'new' subjects.

If a subject withdraws before allocation of a subject number:

- The replacement will be regarded as a 'new' subject and therapy allocated accordingly.

If a subject withdraws after allocation of a subject number:

- The replacement will be allocated to the same randomisation as the subject to be replaced, but will be allocated a new subject number.

The new (replacement) number is attributed by the statistician responsible for randomisation and the corresponding medication shipped to the site.

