7.5 Assignment to Treatment

Subjects will be assigned to one of the two treatments according to a computerised randomisation schedule. When the randomisation number and treatment assignment are obtained, the randomisation number will be recorded on the CRF. This is a single blinded study. The Investigator will be informed of the treatment at the time of randomisation.

Randomisation is performed via an interactive web-based system.

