## 2. STUDY POPULATIONS

Four subject populations will provide the basis for all statistical analyses, data evaluations and summaries of the adult subjects.

Safety Population: The safety population includes all subjects who received at least one dose or partial dose of study drug, with treatment assignment designated according to actual treatment received.

Actual treatment received is not collected in the study database. [REDACTED] [REDACTED] will record the details of any subject receiving treatment that does not correspond to their randomised treatment assignment. Actual treatment received will be defined as being equal to randomised treatment assignment for a particular subject unless the incorrect treatment was administered for the majority of the subject's time on treatment.

Intent-to-Treat (ITT) Population: The intent-to-treat population includes all randomised subjects, according to the randomised treatment assignment. The ITT population will be the primary population of interest for efficacy analyses.

Per-Protocol (PP) Population: The per-protocol population includes all randomised subjects, according to the randomised treatment assignments who have no major protocol deviations (see [Appendix II](#)) and satisfactorily complete the study. The PP population will be a subset of the ITT population and will be the secondary population of interest for efficacy analyses.

Subjects to be excluded from the PP Population will be defined prior to the database lock according to criteria as per [Appendix II](#) without regard to study drug assignment. [Appendix II](#) describes the major protocol deviations affecting the statistical analysis of the study and their derivation; an extensive tracker of all clinical protocol deviations is maintained separately by [REDACTED].

---

Pharmacokinetic (PK) Population: The PK population will consist of all subjects who received the study drug and for whom the primary PK data are considered to be sufficient and interpretable. The PK analysis will utilize the PK population.

Adolescent subject data will be described separately from the adult subjects. There will be no formal statistical analysis of adolescent data, only listings. Data for adolescent subjects will be grouped separately from adult subject data within the listings.

---

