### 6.1.4 Determination of Sample Size

The primary endpoint of time-to-response of blood markers (defined as time-to-response) is monitored in a survival setting. The time-to-response of blood markers comprises recovery of platelets  $\geq 150,000/\mu\text{L}$ . Accrual period was taken as 1.5 years. Actual accrual time is longer than 1.5 years; however there is no impact on the sample size. Zero to time to event period is set at 30 days. As median time-to-response for the control group we take 6 days (this information is calculated based upon Bandarenko *et al.*). For the treated group with ALX-0081 we assume a 44% risk reduction corresponding to a reduction in median time to event of 2.64 days, and ultimately resulting in a time-to-response of 3.36 days. The hazard ratio is defined in the SAS code as the ratio of control versus experimental (ALX-0081) treatment thus equaling to  $6/3.36=1.786$ . The sample size calculations are performed based on a log-rank test, aiming for a power of 80%, tested 1-sided at 2.5% significance level with 1:1 randomisation. Note that we assume that 15% of subjects would be lost-to-follow-up. The latter is justifiable because the active follow-up period (time of first study drug administration to time to event) only

---

equals 30 days. Based on the above described assumptions a sample size of 110 adult subjects is required. As subjects can be replaced, the ITT population may be larger than 110 subjects.

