**Table 1: Censoring/event scenarios (for ITT and PP analysis of confirmed platelet response)**

Case	Description	Time at risk/ Time to recovery of platelets (days)	Responder	Censored (No = 0; Yes = 1)
1	No event in 30 days of continuous daily PE a	30	No	1
2	At day 30, confirmed recovery of platelets (per protocol)	30	Yes	0

Case	Description	Time at risk/ Time to recovery of platelets (days)	Responder	Censored (No = 0; Yes = 1)
3	At day x b (1 st measurement of platelet recovery), confirmed recovery of platelets, ideal case (per protocol)	x	Yes	0
4	No event occurred and subject is no longer in trial at day x b (including replaced subjects who are dosed)	x	No	1
5	At day x b (1 st measurement of platelet recovery), subject has recovery of platelets, however, missing data at 48 hours later, and no subsequent confirmation on platelet count during daily PE (no more daily platelet measurements) c	x	No	1
6	No recovery of platelets, however, daily PE stopped (daily PE considered surrogate for response d ). Except if PE stopped due to AE e (then idem case 4)	Time of last daily PE	No	1
7	Subject not dosed (after randomisation)	1	No	1

a PE = plasma exchange.

b At day x within 30 days assessment period.

c No subsequent confirmation during daily PE, since daily PE has been stopped by Investigator for clinical response which does not meet protocol definition of response.

d Certain subject's platelet counts 'hover' around 150,000/ $\mu$ L, and in clinical practice, PE is stopped.

e Start and stop dates of adverse events related to PE will need to be compared to PE stop dates in order to identify PE stopped due to AE.

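### Subjects who replace a withdrawal after number allocation inherit that subject's arm, and no planned analysis shows the primary result without them

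*Protocol*

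**What the plan says.** Protocol 5.4.3 has two routes. A subject replacing someone who left before receiving a subject number is treated as new and assigned in the ordinary way. After number allocation the rule differs: "The replacement will be allocated to the same randomisation as the subject to be replaced, but will be allocated a new subject number". The statistician responsible for randomisation issues the new number, and the matching medication goes to the site. Whether to replace is decided case by case with the sponsor, with one firm limit: "Subjects withdrawn due to adverse drug reactions or adverse events will not be replaced".

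Protocol 7.5 describes a web-based system for assignment and states: "The Investigator will be informed of the treatment at the time of randomisation".

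SAP section 2 defines the primary set: "The intent-to-treat population includes all randomised subjects, according to the randomised treatment assignment". The PP set also requires that subjects have no major deviation "and satisfactorily complete the study". SAP 6.1.4 adds: "As subjects can be replaced, the ITT population may be larger than 110 subjects". In SAP 6.3.1, Table 1, withdrawn originals stay in the analysis as censored: case 4 covers those who were dosed ("including replaced subjects who are dosed") and case 7 those who were not. SAP 6.2.1 puts replaced subjects in the disposition listing, and SAP section 7 sorts listings by treatment group.

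**The concern.** A replacement on the second route has no random assignment of its own. An investigator whose subject withdrew already knows the arm attached to that slot, and neither document says how the arm is kept from whoever enrols next. Concealment is thus unprotected. It is not shown to be lost: the documents do not say that the replacement comes from the same site, or that a site is told in advance.

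If a site does choose whom to enrol into a known slot, those subjects enter the one confirmatory test, the one-sided log-rank test at 2.5%. The SAP follows the outgoing subject but not the incoming one. A reader could not tell which subjects in the primary analysis lacked their own random assignment, or whether the result depends on them.

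**Working it through.** **Do the planned analyses remove same-arm replacements?** SAP 6.3.1 lists four kinds of sensitivity analysis.

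- PP set: does not remove them. The completion requirement drops withdrawn originals, while no deviation category shown in Appendix II drops a same-arm replacement. PP therefore leans the wrong way.
- Covariate-adjusted Cox model: keeps them.
- Non-confirmed plus confirmed response: keeps them.
- Censoring at start of rituximab: keeps them.

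**Does the sample size depend on replacement?** Inputs from Protocol 10.4: medians of 6 and 3.36 days, one-sided 2.5%, 80% power, 1:1 allocation, 15% loss.

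- Hazard ratio = 6/3.36 = 1.786.
- Events = 4 × (1.960 + 0.842)² / (ln 1.786)² = 93.4.
- Subjects = 93.4/0.85 = 109.9, which reproduces the stated 110.

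The 110 already pays for 15% loss, so replacement is not needed to reach 80% power.

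**How far could type I error move?** Assumptions for the simulation:

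- No true effect, exponential times with median 6 days, 55 per arm, follow-up to 30 days.
- *k* originals (half per arm) censored uniformly over 0 to 30 days, and *k* same-arm replacements added.
- A selected replacement has its response hazard multiplied by *r* on ALX-0081 and divided by *r* on placebo. The between-arm hazard ratio among selected replacements is then *r*²: 1.25² = 1.56 and 1.5² = 2.25.
- 200,000 trials per cell; Monte Carlo standard error √(0.025 × 0.975/200,000), about 0.04 percentage points.

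One-sided type I error; where two figures are given they are for *r* = 1.25 / *r* = 1.5. With no replacements it is 2.6%.

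| *k* | No selection | A quarter selected | Half selected | ALX-0081 slots only | All selected |
|---|---|---|---|---|---|
| 4 | 2.7% | 2.8 / 2.9% | 2.9 / 3.1% | 2.9 / 3.1% | 3.2 / 3.7% |
| 8 | 2.6% | 2.8 / 3.2% | 3.1 / 3.7% | 3.1 / 3.5% | 3.7 / 4.8% |

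Excluding the replacements gives 2.6 to 2.8% in every cell.

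Two variations:

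- Test stratified by prior PE (assumed: 35% with prior PE, hazard × 1.3; 100,000 trials), *k* = 8, *r* = 1.5: 3.6% with half selected, 4.7% with all selected, 2.6 to 2.7% with replacements excluded.
- Withdrawals at day 0 to 3 instead of day 0 to 30, all replacements selected (20,000 trials per cell): at *r* = 1.25 and 1.5, 3.2 and 3.6% for *k* = 4, and 3.5 and 5.1% for *k* = 8. The extreme corner, *k* = 16 and *r* = 2, gives 15.2%.

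**What does replacement buy?** Simulated power at hazard ratio 1.786, with no selection and no other loss (100,000 trials):

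- *k* = 4: 85.5% with replacements, 84.2% without; gain 1.3 points.
- *k* = 8: 86.3% with, 83.8% without; gain 2.5 points.

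**The case against.** The strongest case on the other side is that the mechanism has little room to work. These are emergency patients, screened within 12 hours of the first on-study PE. With 110 subjects over about 53 sites, a site enrols about two (110/53 = 2.1). To bias the test, a site would need a slot of known arm, then a new acute patient, then a forecast of platelet recovery within hours, and would have to accept or decline on that basis. Withdrawals for adverse events are not replaced, the replacement number is issued centrally, and there may have been no replacements at all. Protocol 8.1.1 requires a log of why screened patients were not included, which would leave some trace of selective enrolment. The covariate-adjusted model would absorb selection that acts through the listed baseline features. The worst case needs a hazard ratio of 2.25 from selection alone, more than the 1.786 assumed for the drug.

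Much of this stands as an argument about size. Inheritance without selection does no visible harm, and the upper figures reflect chosen inputs. A count of replaced subjects by arm can also be read from the sorted disposition listing.

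It does not remove the point. Central issue of a number does not hide an arm the investigator already knows. A screening log and covariate adjustment neither restore chance assignment nor show the result without these subjects, and the adjusted model retains only significant covariates. Consent withdrawal, loss to follow-up and withdrawal for protocol violation remain replaceable. SAP section 2 requires PP exclusions to be settled irrespective of arm; no such condition is set for the decision to replace.

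**Conclusion.** The concern holds. Same-arm replacement departs from random assignment, concealment of the slot is unprotected, and the plan neither flags the incoming subjects nor shows the primary result without them. Retaining the withdrawn originals in ITT is correct and should not change.

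The likely effect is small: a few tenths of a percentage point on a 2.5% test with a handful of replacements and partial selection, and about 5% with eight replacements all selected. These figures rest on an assumed number of replacements, an assumed strength of selection and exponential response times. Against that, the rule brings only a point or two of power that the plan does not need. The plan should be changed, mainly because the analysis part of the change costs so little.

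**What to change.** **SAP, before database lock.** Keep every originally randomised subject in ITT. Flag each same-arm replacement and report their number by arm. Add one sensitivity analysis of the primary log-rank test that excludes same-arm replacements and keeps the originals. Cost: one flag, one count and one extra analysis. If there were no replacements, one sentence in the study report settles it.

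**Protocol, for any further enrolment.** Delete same-arm replacement. Either do not replace randomised subjects, or give each added subject a fresh 1:1 assignment through the existing web-based system. Cost: an amendment across about 13 countries, plus system configuration if fresh assignment is chosen. A slight arm imbalance is possible but costs almost nothing: with 93.5 events (110 × 0.85), power is 80.0% at 55:55 and 79.7% at 60:50.

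The amendment cannot repair past enrolment. SAP 6.1.4 already notes "Actual accrual time is longer than 1.5 years; however there is no impact on the sample size", and the documents do not say how many subjects remain to be enrolled. The SAP change is the part that covers those already in the trial, and it is worth making on its own.

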6. STUDY DRUGS

Study drugs include the anti-vWF Nanobody (ALX-0081) and the matching placebo administered during the course of the study.

6.1 Formulation, Packaging and Labelling

6.1.1 Study Drug Formulation

ALX-0081, anti-vWF Nanobody

ALX-0081 is a clear, colourless solution formulated as a solution for injection. It is provided in sterile, preservative-free, non-pyrogenic, single-use 2R glass vials with injection stoppers and light blue aluminum crimped caps. One vial contains 2.4 mL solution for injection. One mL solution for injection contains as active ingredient 5 mg of ALX-0081 (INN: caplacizumab).

Excipients

Phosphate buffer solution (pH 7.1):

WFI, KCl, KH_2PO_4 , $\text{Na}_2\text{HPO}_4 \cdot 2\text{H}_2\text{O}$ and NaCl. Glycine (0.2 M) and polysorbate 80 (0.02%) are used to stabilise the protein in the solution.

Placebo

Placebo is provided in 2R glass vials. One vial contains 2.4 mL solution for injection with identical excipients as ALX-0081.

6.1.2 Study Drug Packaging

Ablynx NV will, via a contract manufacturer, supply the following medication:

- Vials containing 2.4 mL solution of 5 mg/mL of ALX-0081
- Matching placebo vials

The study medication will be packed and dispatched in containers. The batch number and the minimal shelf-life will be given on the outer package. A batch release certificate and a GMP-conformity statement will be provided. Study drugs are provided as vials for injection and supplied to the study centre.

6.1.3 Study Drug Labelling

The study drug will be labelled in accordance with applicable regulatory requirements. At the minimum, the following information will be provided:

- Study number (ALX-0681-2.1/10)
- Name and address of Sponsor
- Batch number and vial number
- Volume
- Pharmaceutical form and route of administration (respectively i.v. or s.c.)
- Storage conditions
- Retest or expiry date
- “For clinical trial use only” and “Keep out of reach and sight of children”

6.2 Storage and Stability

ALX-0081 and placebo are delivered and stored deep frozen at -20°C ($\pm 5^{\circ}\text{C}$) in the original outer package to be protected from light. Stability studies showed that ALX-0081 is stable at -20°C for at least 3 years and can therefore be stored under these conditions at the investigative site. ALX-0081 contains no antimicrobial preservatives. The study drug must not be used after the expiry date indicated on the labels of the outer package.

Upon receipt of the study medication, the responsible pharmacist or his/her designee will inspect and count all study medication for completeness. Subsequently, he/she must immediately return the enclosed acknowledgement of receipt form, duly completed and signed (the date of receipt must be noted).

The pharmacist or his/her designee is responsible for storage of the study medication at the study site in an appropriate lockable room at -20°C ($\pm 5^{\circ}\text{C}$). The medication may not be exposed to direct sunlight or to direct warmth given off by heaters and should be protected from moisture.

6.3 Study Drug Preparation and Administration

All study medications will be prepared at the investigational site by a pharmacist or his/her designee.

Study drug preparation and administration during hospitalisation

During hospitalisation, all study medications will be administered by the Investigator or by medically trained personnel under his/her supervision.

ALX-0081 solution for injection is for single use only. Remaining ALX-0081 solution for injection should be discarded. Procedures for proper handling and disposal should be observed.

Study drug preparation for dispensation to subjects, and administration thereafter

Vials will be thawed in a 25°C water bath or at room temperature until all ice has visibly disappeared and inspected prior to dispensation to subjects. Transport of study medication from the hospital to the subject's home should be secured between 2-8°C. The subject should be instructed to keep the study medication cooled within a refrigerator (2-8°C) until use. Injections must be prepared and administered by medically trained personnel.

Vials can be used during 10 days after thawing. All thawed vials and unused injections should be returned to the pharmacy on a weekly basis. Note that returned vials can no longer be used for administration.

For detailed instructions on the preparation of the solution for injection, its administration and disposal please refer to the IB.

6.4 Return of Study Drug

Generally, all unused study drug (medication and packaging) must be returned to the Sponsor on termination of the study and after a drug accountability and reconciliation check. Upon permission/request of the Sponsor, and if allowed by local procedures and regulations, unused study drug may be destroyed on site. The destruction has to be clearly documented, and can only occur after drug accountability and reconciliation check.

Used study medication can be destroyed per institution policy after drug accountability has been checked.

The pharmacist or his/her designee will be responsible for the inventory of all clinical supplies, exercising accepted pharmaceutical practices. An accurate, timely record of the clinical study supply will be maintained. The original Drug Preparation Log and Drug Dispensing and Accountability Log are considered as source data and will be archived at the site.

6.5 Drug Accountability

Supplies of ALX-0081 will be shipped deep frozen at -20°C ($\pm 5^{\circ}\text{C}$) to the hospital at appropriate intervals, depending on subject accrual. The Investigator at the study site is responsible for keeping accurate drug accountability records throughout the study regarding the receipt of study drug, the dispensing to the subjects and the return of all used and unused study drug.

A Drug Preparation Log as well as a Drug Dispensing and Accountability and temperature Log must be kept current and should contain the following information:

- In hospital use:
 - Vial number
 - Subject number for whom the drug was prepared
 - Number of injections prepared
 - Date on which drug was dispensed
 - Quantity of the drug administered

- Use at home by the subject:
 - Subject number to whom the drug was dispensed
 - Information on vials dispensed
 - Number of vials dispensed
 - Vial identification numbers dispensed
 - Date of thawing
 - Date of dispensation
 - Vials returned by the subject
 - Name of the person who administered the study drug
 - Date and time of study drug administration
 - Quantity of the drug administered

The inventory must be available for inspection by the monitor.

Generally, at study termination, all unused study medication must be returned to the Sponsor accompanied by the appropriate documentation. Upon permission/request of the Sponsor, and if allowed by local procedures and regulations, unused study drug may be destroyed on site. The destruction has to be clearly documented, and can only occur after drug accountability and reconciliation check. Used study medication can be destroyed per institution policy after drug accountability has been checked.

